5.1. Efficacy endpoints

5.1.1. Primary Prospectively-Defined Clinical Endpoints for Efficacy

5.1.1.1. Febrile Neutropenia AEs

A cycle is considered to have a febrile neutropenia AE if any date between the start and stop date of the AE overlaps with any date between the start of cycle and end of cycle. If an event ends on the cycle start day, it will not be counted as an event in that cycle unless the event also started on that day. For the treatment period, the total number of febrile neutropenia AE events is the number of cycles where at least one febrile neutropenia AE is observed. If a patient did not have any febrile neutropenia AE events, the value of 0 will be assigned to that patient. AEs during the study is captured in the electronic database. The event terms are coded using the Medical Dictionary for Regulatory Affairs (MedDRA Version 20.1) and "FEBRILE NEUTROPENIA" is

a preferred term which can be used to identify the proper AE records. Data handling conventions for missing start and stop dates for AEs are described in [Section 5.2.1](#).

Any occurrence of a febrile neutropenia AE during the treatment period is defined as a binary variable (Yes or No); Yes if total number of febrile neutropenia AE events ≥ 1 is observed, No for other scenarios.

5.1.1.2. **RBC Transfusions**

Within a cycle, a RBC transfusion event is defined as either (1) an actual RBC transfusion, OR (2) eligible for RBC transfusion = hemoglobin < 8.0 g/dL. Therefore, for the treatment period, a total number of RBC transfusions (i.e. a RBC transfusion event = Yes) is obtained as the number of cycles in which there is at least one RBC transfusion event. If a patient did not have any RBC transfusion events, the value of 0 will be assigned to that patient. Hence, the total number of cycles without RBC transfusion is calculated as the total number of treatment cycles received – total number of cycles with RBC transfusion.

To define those cycles where a patient was eligible for a RBC transfusion, the lab value of hemoglobin (< 8.0 g/dL) must fall between start of cycle and end of cycle for that cycle. Any unscheduled data and the actual assessment date (rather than visit date) will be included in the derivation.

Hence, any occurrence of a RBC transfusion during the treatment period is defined as a binary variable (Yes or No); Yes if total number of cycles with RBC transfusion ≥ 1 is observed, No for other scenarios.

5.1.1.3. **Platelet Transfusions**

Similarly, within a cycle, a platelet transfusion event is defined as either (1) an actual platelet transfusion, OR (2) eligible for platelet transfusion = platelet count $\leq 10 \times 10^9/L$. Therefore, for the treatment period, a total number of platelet transfusions (i.e. a platelet transfusion event = Yes) is the number of cycles in which there is at least one platelet transfusion event. If a patient did not have any platelet transfusion events, the value of 0 will be assigned to that patient. Therefore, the total number of cycles without a platelet transfusion is calculated as the total number of treatment cycles received – total number of cycles with platelet transfusion.

To define those cycles where a patient was eligible for a platelet transfusion, the lab value of platelet count ($\leq 10 \times 10^9/L$) must fall between start of cycle and end of cycle for that cycle. Any unscheduled data and the actual assessment date (rather than visit date) will be included in the derivation.

Hence, any occurrence of a platelet transfusion during the treatment period is defined as a binary variable (Yes or No); Yes if total number of cycles with platelet transfusion ≥ 1 is observed, No for other scenarios.

5.1.1.4. **GCSF Administrations**

Administration of GCSF is collected with the concomitant medications which are coded using World Health Organization Drug Dictionary (WHO-DD Version Sep2017). The criterion to select proper records is as follows: If the chemical subgroup from WHO-DD Version Sep2017 (i.e. TEXT4 for CODE4) takes value “COLONY STIMULATING FACTOR”, the medication is classified as GCSF.

A cycle where GCSF is administered concurrently will be identified by comparing the start and stop dates of each administration of GCSF to the start of cycle and end of cycle. If any of the dates of administration of GCSF overlap with any dates between the start of cycle and end of cycle, that cycle will be considered as having GCSF administered. Data handling conventions for missing start and stop dates are described in [Section 6.2.5](#).

For the treatment period, the total number GCSF administration is the number of cycles in which there is at least one GCSF dose administered. If a patient did not have any GCSF use, the value of 0 will be assigned to that patient. The number of cycles where GCSF was NOT given is calculated as total number of treatment cycles received – total number of cycles where GCSF was administered.

Therefore, any occurrence of a GCSF administration during the treatment period is defined as a binary variable (Yes or No); Yes if total number of cycles with GCSF administration ≥ 1 is observed, No for other scenarios.

5.1.1.5. **ESA Administrations**

Administration of erythropoiesis stimulating agents (ESAs) is collected with the concomitant medications which are coded using WHO-DD Version Sep2017. The criterion to select proper records is as follows: If the chemical subgroup from WHO-DD Version Sep2017 (i.e. TEXT4 for CODE4) takes value “OTHER ANTIANEMIC PREPARATIONS”, the medication is classified as ESAs. If a patient did not receive an ESA, then the patient will be set to 0.

Those cycles where ESAs are administered concurrently will be identified by comparing the start and stop dates of each ESA to the start of cycle and end of cycle. If any of the dates of administration of an ESA overlap with any dates between the start of cycle and end of cycle, that cycle will be considered as having an ESA administered. Data handling conventions for missing start and stop dates are described in [Section 6.2.5](#).

For the treatment period, the total number GCSF administration is the total number of cycles in which there is at least one ESAs dose administered;. If a patient did not have any ESA use, the value of 0 will be assigned to that patient. The number of cycles where ESAs were NOT given is calculated as total number of treatment cycles received – total number of cycles where ESAs were administered.

Therefore, any occurrence of an ESAs administration during the treatment period is defined as a binary variable (Yes or No); Yes if total number of cycles with ESAs administration ≥ 1 is observed, No for other scenarios.

5.1.1.6. **IV Antibiotic Uses**

IV antibiotic administration is collected with concomitant medications which are coded using WHO-DD Version Sep2017. The criteria for identifying an IV antibiotic administration event is

- If the Therapeutic subgroup from WHO-DD Version Sep2017 (i.e. TEXT2 for CODE2) takes value “ANTIBACTERIALS FOR SYSTEMIC USE”, and
- The route of medication is “intravenous” or the route is “other” with the detailed specification as “IVPB”.

Those cycles where IV antibiotics are administered concurrently will be identified by comparing the start and stop dates of each antibiotic to the start of cycle and end of cycle. If any of the

dates of administration of any IV antibiotic overlap with any dates between the start of cycle and end of cycle, that cycle will be considered as having an IV antibiotic administered. Data handling conventions for missing start and stop dates are described in [Section 6.2.5](#).

For the treatment period, the total number IV antibiotics administration is the total number of cycles where IV antibiotics were administered. If a patient did not have any IV antibiotic use, the value of 0 will be assigned to that patient. The number of cycles where IV antibiotics were NOT given is calculated as total number of treatment cycles received – total number of cycles where IV antibiotics were administered.

Therefore, any occurrence of an IV antibiotics administration during the treatment period is defined as a binary variable (Yes or No); Yes if total number of cycles with IV antibiotics administration ≥ 1 is observed, No for other scenarios.

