### **8.7. Transfusions**

Platelets should be transfused at a threshold of  $\leq 10,000/\mu\text{L}$ . Platelets should also be transfused in any patient who is bleeding with a platelet count  $< 50,000/\mu\text{L}$  ( $100,000/\mu\text{L}$  for central nervous system or ocular bleeding). Please also refer to the American Society of Clinical Oncology (ASCO) guidelines ([Smith 2006](#)).

Patients with hemoglobin  $< 8.0$  g/dL or with symptomatic anemia can be treated with RBC transfusions at the investigators discretion.

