  - Incidence of infections overall and by severity
  - Incidence of RBC and platelet transfusions
  - Incidence of hematopoietic growth factors use
  - Incidence and duration of systemic antibiotic use
  
- Exploratory efficacy endpoints:
  - Incidence of Grade 2 or greater nephrotoxicity
  - Incidence of alopecia and mucositis
  - Functional Assessment of Cancer Therapy QOL instrument (FACT) total scale score (general)
  - FACT domain scores (physical, social/family, emotional, and functional well-being)
  - FACT-L total scale score
  - FACT-L lung cancer subscale score
  - FACT-L trial outcome index score
  - FACT-An total scale score
  - FACT-An anemia subscale score
  - FACT-An trial outcome index score
  - Composite hematologic score (this will be specified *a priori* in a SAP)
  - Composite efficacy score (this will be specified *a priori* in a SAP)

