2. STUDY DETAILS

2.1. Study Objectives

The primary, secondary, and exploratory objectives of this study are presented in [Table 1](#).

Table 1 G1T28-02: Study Objectives

	Phase 1b Dose-Finding Portion of Part 1	Phase 2a Expansion Portion of Part 1	Phase 2a Part 2
Primary Objectives			
Assess the DLTs and define the Phase 2 dose of G1T28 administered with E/P therapy	X		
Assess the safety and tolerability of G1T28 administered with E/P therapy	X	X	X
Secondary Objectives			
Assess the PK profile of G1T28	X		
Assess the PK profile of etoposide and carboplatin when administered with G1T28	X		
Assess the hematologic profile (kinetics and incidence/duration/frequency of toxicities) of G1T28 administered with E/P therapy	X	X	X
Assess the incidence of febrile neutropenia	X	X	X
Assess the incidence of infections	X	X	X
Assess the utilization of RBC and platelet transfusions	X	X	X
Assess the utilization of hematopoietic growth factors	X	X	X
Assess the utilization of systemic antibiotics	X	X	X
Assess the incidence of chemotherapy dose reductions and dose interruptions overall	X	X	X
Assess the incidence of Grade 2 or greater nephrotoxicity	X	X	X
Assess tumor response based on RECIST, Version 1.1	X	X	X
Assess PFS and overall survival	X	X	X
Exploratory Objectives			
Assess the incidence of mucositis	X	X	X
Assess the incidence of alopecia	X	X	X
Assess the incidence of fatigue	X	X	X
Assess patient-reported QOL	X	X	X
Assess immunologic markers			X

DLT = dose-limiting toxicity; E/P therapy = etoposide + carboplatin on Day 1 and etoposide on Days 2 and 3 of 21-day cycles; PFS = progression-free survival; PK = pharmacokinetic; QOL = quality of life; RBC = red blood cell; RECIST = Response Evaluation Criteria in Solid Tumors

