6.2.7.1. Prospectively-Defined Efficacy Analyses

Detailed information for the prospectively-defined efficacy endpoints can be found in [Section 5.1.1](#). A binary response variable (Yes, No) will be analyzed to compare G1T28 and placebo using stratum-adjusted method to account for the ECOG status (0-1 vs 2) as the stratification factor. The adjusted proportion difference (trilaciclib vs placebo) and its 80% CIs will be calculated using CMH weight outlined in [Kim et al. 2013](#). The two-sided p-value will be calculated using stratified exact Cochran-Mantel-Haenszel (CMH) method. The following binary response variables will be analyzed:

- Occurrence of a febrile neutropenia AE during the treatment period (refer to [Section 5.1.1.1](#));
- Occurrence of a RBC transfusion (actual and eligible) during the treatment period (refer to [Section 5.1.1.2](#));
- Occurrence of a platelet transfusion (actual and eligible) during the treatment period (refer to [Section 5.1.1.3](#));
- Occurrence of a GCSF administration during the treatment period (refer to [Section 5.1.1.4](#));

- Occurrence of an ESA administration during the treatment period (refer to [Section 5.1.1.5](#));
- Occurrence of an IV antibiotic administration during the treatment period (refer to [Section 5.1.1.6](#));
- Occurrence of an infection SAE during the treatment period (refer to [Section 5.1.1.7](#));
- Occurrence of a pulmonary infection SAE during the treatment period (refer to [Section 5.1.1.7](#)).

Time (days) to event endpoints will be summarized using Kaplan-Meier method, and the descriptive statistics of median, 25% and 75% percentiles along with their 95% CIs will be calculated for endpoints described in [Sections 5.1.1.8, 5.1.1.9, and 5.1.1.11](#).

In addition to the summary from Kaplan-Meier method, for the endpoints of

- Overall duration (days) of Grade 4 neutropenia;
- Overall duration (days) of Grade 3/4 neutropenia;
- Time (days) to first occurrence of a MAHE event,

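### The SAP's transfusion endpoints also count untransfused patients who meet a laboratory threshold, and no actual-only analysis is specified, so the transfusion-utilization objective has no dedicated estimate

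*SAP*

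**What the plan says.** **Objective and protocol endpoint.** The secondary objective in Protocol Table 5-1, repeated in SAP 2.1, is "Assess the utilization of RBC and platelet transfusions". Protocol 13.4.1 lists the endpoint as "Incidence of RBC and platelet transfusions". Protocol 13.4.2.4 analyses it as the number and percentage of patients, with a between-arm difference in Part 2. Neither section has an eligibility component.

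**SAP definition.** In SAP 5.1.1.2, "a RBC transfusion event is defined as either (1) an actual RBC transfusion, OR (2) eligible for RBC transfusion", the second limb being set as "eligible for RBC transfusion = hemoglobin < 8.0 g/dL". In SAP 5.1.1.3, "a platelet transfusion event is defined as either (1) an actual platelet transfusion, OR (2) eligible for platelet transfusion = platelet count" at or below 10 × 10^9/L.

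**Where the definition goes.** The composite is the only transfusion variable in Table 3, in the major adverse hematologic event (MAHE) components (Tables 3 and 5) and in the stratified comparison of Section 6.2.7.1. That section lists "Occurrence of a RBC transfusion (actual and eligible) during the treatment period" and the platelet equivalent. The per-patient totals in 5.1.1.2 and 5.1.1.3 count cycles with a composite event, so they carry the same mixture.

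**Transfusion rule.** Protocol 8.7 says that patients with hemoglobin below 8.0 g/dL or symptomatic anemia "can be treated with RBC transfusions at the investigators discretion". For platelets, the same section directs transfusion at the threshold.

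**Declared changes.** SAP Section 7 lists endpoints and analyses removed from the protocol. It neither lists transfusion incidence as removed nor mentions the composite.

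**The concern.** Utilization means transfusions given. Under the SAP, a patient with one hemoglobin value below 8.0 g/dL and no transfusion is recorded as a transfusion event. That value is Grade 3 in the SAP's own Table A-1, so the RBC endpoint is in effect transfused or Grade 3 laboratory anemia. A result reported as the proportion with RBC transfusion would mix a treatment with a laboratory toxicity. A between-arm difference could come from either component, or from both.

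The SAP also treats similar endpoints differently. The G-CSF, ESA and IV antibiotic endpoints (5.1.1.4 to 5.1.1.6) count actual administration only, although Protocol 8.4.4.2 gives a hemoglobin level for ESA use and neutrophil triggers for G-CSF. Only the transfusion endpoints count patients who were not treated.

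At stake is whether the trial answers a stated secondary objective with an estimate and an interval, or leaves readers to piece it together from other outputs.

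**Working it through.** **1. The plan's own figure.** SAP 2.3 gives only per-arm precision at n = 35. The Wilson half-width is z/(1 + z²/n) × √[p(1−p)/n + z²/(4n²)]. With z = 1.96, n = 35 and p = 0.5, this is (1.96/1.1098) × √(0.007143 + 0.000784) = 0.157, as stated. The continuous figure, t(0.975, 34)/√35 = 0.3435, matches the stated 0.344. Neither depends on how a transfusion is defined. The documents give no transfusion rate, eligible-only rate or power.

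**2. Direction in one arm.** Let A be the proportion actually transfused and E the proportion who met the threshold but were never transfused. The composite is C = A + E, so C ≥ A always. Part 2 randomizes 70 patients 1:1, so each eligible-only patient adds 1/35 = 2.9 points to an arm; two add 5.7 and five add 14.3.

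**3. Direction of the arm difference.** C(placebo) − C(active) = [A(placebo) − A(active)] + [E(placebo) − E(active)]. Equal E leaves the difference unchanged; unequal E widens or shrinks it. For illustration, **assume** actual rates of 25% (placebo) and 10% (active). Power is for an unstratified two-proportion test with 35 per arm at two-sided 0.20, the SAP's level.

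| Assumed E, placebo / active | C, placebo / active | Difference (points) | Power |
|---|---|---|---|
| 0 / 0 (actual only) | 25% / 10% | 15 | 0.647 |
| 5% / 5% | 30% / 15% | 15 | 0.589 |
| 10% / 10% | 35% / 20% | 15 | 0.550 |
| 15% / 15% | 40% / 25% | 15 | 0.523 |
| 15% / 5% | 40% / 15% | 25 | 0.865 |
| 5% / 15% | 30% / 25% | 5 | 0.208 |

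With assumed actual rates of 20% and 10%, the same two unequal patterns turn a 10-point difference into 20 points or 0.

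**4. Can A be recovered from other planned tables?** SAP 6.2.8.2 tabulates any Grade 3 or 4 laboratory value during treatment. For hemoglobin, Table A-1 has no Grade 4, so this is the proportion G with a value below 8.0 g/dL. If the populations and windows match, C − G is the proportion transfused without such a value. E is still unknown, because G does not separate transfused from untransfused patients. A is therefore only bounded: C − G ≤ A ≤ C.

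**The case against.** The strongest case for the SAP has five parts.

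- **Actual use may be visible elsewhere.** Protocol 8.6 records blood products with concomitant medications, SAP 6.2.5 summarizes these by number and percentage of patients, and Section 6.2.7 promises supporting listings. A reader might infer that transfusion use goes wholly unreported; the documents do not support that. What remains is that those summaries, by preferred term and ATC class, carry no stratified difference or interval. The SAP also does not say which form or coding supplies transfusion records.
- **The low-value component is tabulated.** A reader might infer that the two components can never be told apart. For RBC that goes too far: Grade 3 hemoglobin is summarized, and hemoglobin over time is a prospectively defined analysis. As step 4 shows, this bounds the actual rate without giving it.
- **The composite is openly labelled** in Table 3, Table 5 and Section 6.2.7.1. This stands. It tells readers that the number is not pure utilization, but does not supply the missing number.
- **A uniform laboratory criterion is defensible.** With discretionary RBC transfusion at up to 80 centers, it limits variation in local practice. This is a good reason to keep the composite, but not to omit the actual rate. Blinding in Part 2 also limits arm-related bias in discretionary transfusion.
- **The platelet case is weaker.** The protocol directs transfusion at the SAP's platelet threshold, so an eligible-only case would be a departure from that instruction. This stands.

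In addition, Section 7 describes its list as removals, so an altered definition falls outside its literal scope. Recording it there is good practice rather than correction of a false statement.

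**Conclusion.** The point holds as a gap in the SAP. The protocol's transfusion incidence has been replaced by an actual-or-eligible composite, the change is not declared, and no actual-only variable or comparison is specified. The protocol's own incidence analysis is not listed as dropped, so the two documents are out of step on this endpoint.

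The certain part of the size is the direction within an arm: the composite rate is never below the actual rate, and rises by 2.9 points per eligible-only patient. Any total, such as 5 to 15 points, only restates an assumed eligible-only rate.

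A reader might infer that the composite biases the comparison in favor of G1T28. The documents do not show this. Equal eligible-only rates leave the difference unchanged, and unequal rates can move it either way. The SAP's hypothesis that the drug preserves red cells makes unequal rates plausible, not demonstrated.

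The concern applies mainly to RBC. It is a worthwhile and inexpensive improvement, not a flaw that undermines the trial.

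**What to change.** 1. Add actual-only RBC and actual-only platelet transfusion (any occurrence during the treatment period) as the estimates for the utilization objective. Use the same stratified CMH method and 80% interval as in Section 6.2.7.1. Report the number of cycles with an actual transfusion alongside.
2. Show the eligible-only component by arm for each product, so that the composite can be decomposed.
3. Keep the actual-or-eligible composite as a separately labelled endpoint, and leave it in MAHE.
4. Name the data source and selection rule for actual transfusions, as the SAP does for G-CSF and ESA.
5. Record the change of definition in Section 7.

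No new data are needed, because actual transfusions are already an input to the derivation. The cost is a few table rows and two additional comparisons, each at the SAP's nominal two-sided 20% level, in a plan that already tests many endpoints. No change to any transfusion threshold is proposed.

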5.1.1.7. Infection SAEs and Pulmonary Infection SAEs

Each infection SAE and pulmonary infection SAE is captured in the electronic database. The event terms are coded using the MedDRA Version 20.1. The criterion for identifying the proper infection SAE and pulmonary infection SAEs records is as follows: if the system organ class (SOC) from MedDRA takes value “INFECTIONS AND INFESTATIONS”, the preferred term (PT) takes values from [Table 4](#), and the AE is a serious event.

Table 4 PT List for Grouping Infection AEs and Pulmonary Infection AEs

Category	Preferred terms	
Pulmonary Infection AEs	Bronchitis	
	Influenza	
	Pneumonia	
	Pneumonia bacterial	
	Respiratory tract infection	
	Upper respiratory tract infection	
	Viral upper respiratory tract infection	
Infection AEs	Anal abscess	Oral herpes
	Bacteraemia	Pharyngitis streptococcal
	Bronchitis	Pneumonia
	Candida infection	Pneumonia bacterial
	Chronic sinusitis	Respiratory tract infection
	Conjunctivitis	Sepsis
	Infection	Skin infection
	Influenza	Upper respiratory tract infection
	Nasopharyngitis	Urinary tract infection
	Oral candidiasis	Urosepsis
		Viral upper respiratory tract infection

A cycle is considered to have an infection SAE if any date between the start and stop date of the AE overlaps with any date between the start of cycle and end of cycle. If an event ends on the

cycle start day, it will not be counted as an event in that cycle unless the event also started on that day. For the treatment period, the total number of infection SAE events is the number of cycles where at least one infection SAE is observed. If a patient did not have any infection SAE events, the value of 0 will be assigned to that patient. Data handling conventions for missing start and stop dates for AEs are described in [Section 5.2.1](#).

Any occurrence of an infection SAE during the treatment period is defined as a binary variable (Yes or No); Yes if total number of infection SAE events ≥ 1 is observed, No for other scenarios.

Similarly, a cycle is considered to have a pulmonary infection SAE if any date between the start and stop date of the AE overlaps with any date between the start of cycle and end of cycle. If an event ends on the cycle start day, it will not be counted as an event in that cycle unless the event also started on that day. For the treatment period, the total number of pulmonary infection SAE events is the number of cycles where at least one pulmonary infection SAE is observed. If a patient did not have any pulmonary infection SAE events, the value of 0 will be assigned to that patient. Data handling conventions for missing start and stop dates for AEs are described in [Section 5.2.1](#).

Any occurrence of a pulmonary infection SAE during the treatment period is defined as a binary variable (Yes or No); Yes if total number of pulmonary infection SAE events ≥ 1 is observed, No for other scenarios.

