Proportion of patients with infectious SAEs during the treatment period
Proportion of patients with pulmonary infectious SAEs during the treatment period
Time to first major adverse hematologic event (MAHE) which is defined to include components as the following: 
 • hospitalization for a hematologic event (e.g. febrile neutropenia, thrombocytopenia, hemoptysis, etc.) • febrile neutropenia • death related to treatment (including backbone chemotherapy and trilaciclib) • dose delay/reduction due to ANC or platelet counts • duration of Grade 4 ANC > 5 days

G1 Therapeutics, Inc.
Clinical Study Protocol G1T28-02

Statistical Analysis Plan
Version date: 14Feb2018

- RBC transfusion (actual or eligible)
- platelet transfusion (actual or eligible)

ANC = absolute neutrophil count; ESA = erythropoiesis stimulating agent; GCSF = granulocyte-colony stimulating factor; IV = intravenous; NADIR = the lowest point; SAEs = serious AEs.

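### Infection and pulmonary infection SAEs count only if the preferred term is on a fixed list, so a patient whose only serious infection carries an unlisted term is scored as having none

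*SAP*

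**What the plan says.** SAP 5.1.1.7 sets one rule with three joint conditions: the system organ class (SOC) is "INFECTIONS AND INFESTATIONS", "the preferred term (PT) takes values from" Table 4, "and the AE is a serious event". Table 4 is headed "PT List for Grouping Infection AEs and Pulmonary Infection AEs".

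A cycle has an event if any day of a qualifying event overlaps that cycle. For patients with no qualifying event the SAP states "If a patient did not have any infection SAE events, the value of 0 will be assigned to that patient" and, for the lung subset, "If a patient did not have any pulmonary infection SAE events, the value of 0 will be assigned to that patient". Each binary endpoint is Yes with one or more such cycles and No otherwise.

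The endpoint is named more broadly elsewhere. SAP Table 3 calls it "Proportion of patients with infectious SAEs during the treatment period". Protocol 13.4.1 has "Incidence of infections overall and by severity". Neither restricts the terms. SAP section 7, which lists what was removed from the protocol's analyses, drops the by-severity summary and the exposure-adjusted infection rate but does not mention a term restriction.

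Both endpoints are compared between arms in Part 2 by an exact CMH test stratified by ECOG status (SAP 6.2.7.1), at a two-sided 20% level (SAP 6.1.1), with 35 patients planned per arm (SAP 2.3).

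**The concern.** The name of the endpoint and its derivation do not match. A reader of Table 3 expects every serious infection to count. Under 5.1.1.7 a serious event that MedDRA places in the infection class does not count if its preferred term (PT) is missing from Table 4, and the patient is then recorded as infection-free unless a listed event also occurs.

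This is a stated rule that can misclassify patients, not a missing detail. With 35 patients per arm and an endpoint limited to serious events, the counts may be small, so one or two misclassified patients could visibly alter the estimate and the p-value.

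**Working it through.** There is no stated figure to reproduce. The check is the logic of the rule, a count of the list, and an illustration on assumed counts.

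**1. The list.** Table 4 has 21 infection PTs and 7 pulmonary PTs, and all 7 are among the 21. There is no row for other terms, no wording that marks the entries as examples, and no update or review step.

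**2. What the PT condition does.** Let S be the serious events in the infection SOC that overlap a cycle, and L the events with a listed PT.
- Infection endpoint: the events counted are S ∩ L, which is a subset of S. Since S already is the set of infection SAEs, the condition can remove events and can never add one.
- Pulmonary endpoint: the SOC is wider than lung infection, so some list is required. What is missing is a rule for a PT that is not on it.

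**3. Result by type of patient.**

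| Serious infections in the treatment period | Infection endpoint | Pulmonary endpoint |
|---|---|---|
| At least one listed pulmonary PT | Yes | Yes |
| Only an unlisted PT, lung infection | No (wrong) | No (wrong) |
| Only an unlisted PT, not lung | No (wrong) | No (right) |
| An unlisted PT plus a listed non-pulmonary PT | Yes | No (wrong if the unlisted event is in the lung) |

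**4. How the SAP treats comparable derivations.**
- Hospitalization for a hematologic event, a component of the major adverse hematologic event (MAHE) endpoint (5.1.1.11, Tables 5 and 6): the PTs are offered as suggestions, some are sent to individual medical review, and the review closes before unblinding.
- Best overall response (5.2.6.4): patterns not covered by Table 17 are reviewed before unblinding.
- IV antibiotics (5.1.1.6): a whole therapeutic subgroup plus route, with no list of drugs.

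The infection endpoints have no such fallback.

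**5. Size per patient.** 1/35 = 0.0286, or 2.9 percentage points in that arm and in the difference between arms.

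**6. Direction.** The documents give no infection SAE rates, so the counts below are assumed. The p-values are two-sided Fisher tests with 35 per arm, an unstratified stand-in for the planned stratified exact CMH because the ECOG split is unknown.

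| Trilaciclib vs placebo, of 35 each | Loss assumed | Difference, points | p |
|---|---|---|---|
| 3 vs 8 | none | 5/35 = 14.3 | 0.19 |
| 3 vs 7 | one, placebo | 4/35 = 11.4 | 0.31 |
| 3 vs 6 | two, placebo | 3/35 = 8.6 | 0.48 |
| 2 vs 7 | one per arm | 5/35 = 14.3 | 0.15 |
| 1 vs 8 | two, trilaciclib | 7/35 = 20.0 | 0.03 |

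The p-value can move across 0.20 or further below it, depending on where the losses fall.

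**7. Equal capture in both arms.** If the list captures the same share c of affected patients in each arm, the expected difference is c × (true difference). With assumed true rates of 20% and 10%, c = 0.9, 0.8 and 0.6 give 9, 8 and 6 points in place of 10. On average this shrinks the risk difference; chance decides where one or two lost patients fall.

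**The case against.** The strongest reply is that the list may remove nothing. Its heading refers to AEs and not only SAEs. It contains terms that seem unlikely to be serious (conjunctivitis, nasopharyngitis) and broad ones (Infection, Sepsis, Respiratory tract infection). It could be an enumeration of terms already coded, in which case only terms coded later are at risk. The SAP is late-stage: it names MedDRA 20.1 and reports which doses Part 1 evaluated. This stands as a limit on size. The SAP does not say how the list was built or whether the coded data were complete, so neither reading can be shown.

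Second, unlisted events do not vanish from the report. SAP 6.2.8.1 tabulates SAEs by SOC and/or PT and lists all of them separately, so a mismatch with the endpoint count could be seen. A serious infection treated with IV antibacterials also enters the IV antibiotic endpoint whatever its AE term. This stands too, but it does not correct the endpoint.

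Third, these are 2 of the 17 rows of Table 3, and protocol 13.2.3 calls the study descriptive with no formal hypothesis testing across groups. No decision rule is tied to either endpoint. That limits the weight of crossing 0.20, but a descriptive proportion should still count what its name says.

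A reader might go further and infer that serious infections are in fact being lost, or that the rule favors one arm. The documents support neither. They show no unlisted event, and the list applies identically to both arms.

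**Conclusion.** The rule in SAP 5.1.1.7 is narrower than the endpoint it serves. For infection SAEs the PT condition can only remove true events. For pulmonary infection SAEs a list is justified, but unlisted terms have no route to classification. A patient whose only serious infection is unlisted is scored No on both endpoints, which is always wrong for the first and wrong for the second when the infection is in the lung.

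The effect is 2.9 percentage points per affected patient in an arm of 35, in either direction for the comparison. The number affected is unknown and may be zero, and nothing in the documents narrows it. The Fisher results rest on assumed counts and on a test other than the planned one; they show sensitivity to one or two patients and are not a forecast. The point is worth acting on because the change does nothing if every term is listed and corrects the endpoint if one is not.

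**What to change.** In SAP 5.1.1.7, define an infection SAE as any serious AE in the SOC Infections and Infestations that meets the existing cycle-overlap rule, with no PT condition. Leave the timing rule unchanged. Rewording it in terms of treatment-emergent events would bring in the onset rule of SAP 5.2.1 and drop a serious infection that begins before first dose and continues into Cycle 1, which the present rule counts if its PT is listed.

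For pulmonary infection SAEs, keep the Table 4 pulmonary terms as the starting list. Classify every other PT coded in that SOC as pulmonary or not by documented blinded medical review, finalized before unblinding, as the SAP already does for the MAHE hospitalization terms.

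The cost is one sentence and a short blinded review of coded terms. No new data are needed, and the test and sample size do not change.
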